16.2 Secondary Endpoint Analyses

Analysis Set: ITT/SAF

16.2.1 Progression Free Survival (PFS)

PFS time is defined as the time from the date of first treatment administration to

- o the date of the first documentation of objective PD or
- o death due to any cause within 12 weeks of last tumor assessment,

whichever occurs first.

PFS time will be censored at the date of last adequate tumor assessment for subjects who

o do not have an event (PD or death within, less than or equal to 12 weeks of last adequate tumor assessment).

Last adequate tumor assessment is defined as the last tumor assessment result that is CR, PR, Non-CR/non-PD, or SD.

PFS time will be censored on the date of first study treatment for subjects who do not have

- o a baseline tumor assessment or
- o any post-baseline tumor assessments within, less than or equal to, 12 weeks of first administration of study treatment,

unless death occurred on or before the time of the second planned tumor assessment, in which case the death will be considered an event.

The date of event/censoring is defined as follows:

	Status	Censoring	Date of event / censoring
D	Radiological PD or death within, less than or equal to 12 weeks of last adequate tumor assessment	Event	Minimum (Date of PD, Date of death)
Progressed or died	Otherwise	Censored	Date of last tumor assessment with outcome CR, PR, Non-CR/non-PD, or SD or date of first study drug administration, whatever is later
Neither progressed nor died		Censored	Date of last tumor assessment with outcome CR, PR, Non-CR/non-PD, or SD or date of first study drug administration, whatever is later

PFS (months) = (date of event/censoring – date of first trial treatment administration $+ \frac{1}{30.4375}$

The analysis of PFS per investigator as assessed by RECIST 1.1 and mRECIST will be performed using the following methods:

Kaplan-Meier (i.e. product-limit) estimates of the minimum, maximum, and median PFS time will be presented overall along with 90% CIs for the median calculated according to Brookmeyer

and Crowley (3). In addition, the pattern of censoring will be summarized (e.g. censoring due to death, study withdrawal, lost to follow-up, censoring due to data cut-off).

The number of subjects at risk for death or PD vs. those who have died or experienced progression along with Kaplan-Meier estimates of survival probability at 3, 6, and 12 months will be estimated with corresponding 90% CIs derived using the log-log transformation according to Kalbfleisch and Prentice (4) (i.e. conftype = loglog default option in SAS LIFETEST procedure).

A Kaplan-Meier plot of PFS and a listing of PFS data will be provided. The PFS analyses based on RECIST 1.1described above will be repeated for the subgroups defined in Section 10.

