#### **Treatment Duration**

The trial periods and treatment duration are the same for both Phase Ib and Phase II. Each will contain a screening period of up to 28 days prior to trial treatment, to assess subject eligibility.

At the conclusion of screening, eligible subjects will be enrolled into the trial and will then enter a treatment period, during which subjects will be administered MSC2156119J once daily, in 21-day cycles. Subjects will continue taking MSC2156119J until PD [as assessed by the investigator according to Response Evaluation Criteria in Solid Tumors (RECIST) Version 1.1], intolerable toxicity, death, or withdrawal from treatment. Subjects will be evaluated for efficacy, safety, and PK.

Upon discontinuation from MSC2156119J, subjects will have an end-of-treatment evaluation. A Post-treatment Follow-up Visit will also be performed  $30 \pm 3$  days after the last dose.

A schematic of the flow of events for each subject is displayed in Figure 3.

Abbreviations: DLT, dose-limiting toxicity; IMP, investigational medicinal product. Subjects may repeat cycles without limitation until determination of progressive disease or intolerable toxicity, so that the maximum number of cycles received by an individual subject may be > 3.

Survival data will be collected every 3 months after the Post-treatment Follow-up Visit until death or until the end of the trial, whichever comes first.

The planned trial period is from June 2014 (first subject enrolled) to March 2016 (last subject's last visit).

Trial endpoints are described in Section 8.3.

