# 7.1.3.7 Cycle 3 Day 1 (and Day 1 of All Subsequent Cycles)

The frequency of visits will be every 3 weeks up through Cycle 8. From Cycle 9 onward, the frequency of visits will be every 6 weeks, and after Cycle 13, the frequency of visits will be every 12 weeks. These visits may occur within  $\pm$  5 days of Day 1 of the applicable cycle. Refer to Section 7.1.3.4 for the calculation of Day 1 of each cycle.

The following assessments and examinations will be performed on this day of each cycle for which there is a visit:

- Physical examination including body weight;
- A urine pregnancy test will be completed in women of childbearing potential before administration of the dose. If the pregnancy test is positive, it must be confirmed with a serum pregnancy test.
- ECOG PS;
- Vital signs; ECG (predose only);
- Blood samples (to assess hematology, chemistry, and coagulation);
- Urinalysis;
- Serum AFP;
- Complete tumor assessment using RECIST Version 1.1 and secondarily using mRECIST for HCC (on Day 1 of Cycles 3, 5, 7, 9, 11, 13, and every 4 cycles thereafter until disease progression or study drug discontinuation; can occur within 5 days prior to the start of each of these cycles but must be performed prior to the start of each of these cycles);
- AE assessment;
- Recording of concomitant medications/procedures;
- Tumor assessment by F-FDG PET CT scan (Cycle 3 Day 1 only);
- FHSI-8 and FACT-HP (Phase II only).

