### 8.1 Sample Size

For Phase Ib, the sample size of up to 18 subjects was not based on any statistical assumptions; rather, it follows the "3+3 rule," a well-established current methodology in the design of dose-finding trials in oncology.

For Phase II, the sample size of 48 subjects was determined as follows. Under the assumption of no treatment effect, the rate of MET+ subjects without progression at 12 weeks (the primary endpoint) was assumed to be ~15% based on historical data. It is expected that MSC2156119J treatment will lead to 30% MET+ subjects without progression at 12 weeks. The null hypothesis (that the true rate of subjects without progression at 12 weeks is  $\leq 15\%$ ) will be tested using a one-stage design based on the exact binomial distribution (5). With a type I error rate of 5% (one-sided) if the true rate of subjects without progression at 12 weeks is  $\leq 15\%$ , to reach a power of 80% if the true rate of subjects without progression at 12 weeks is 30%, this design requires 48 subjects to be treated in Phase II.

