16.4.1 Endpoint Analysis per Independent Endpoint Review Committee (IERC)

The PFS, TTP, and BOR per IERC for both RECIST 1.1 and mRECIST will be calculated as a sensitivity analysis to the primary and secondary endpoints. In case of different dates of scans within the same tumor assessment visit, the earliest scan date should be used as the date of tumor assessment.

Overall summary tables per the IERC for both RECIST 1.1 and mRECIST will be produced for PFS and TTP as described in Sections 16.2.1 and 16.2.2, respectively.

Contingency tables for both RECIST 1.1 and mRECIST will be created to compare the following tumor assessment results between IERC and investigators:

• BOR (NE / PD / SD / CR / PR / Non-CR/non-PD / CR + PR)

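### mRECIST and IERC PFS/TTP censor subjects at investigator RECIST 1.1 progression, where scanning stops; this censoring is likely informative, mainly for TTP, and the SAP neither counts nor bounds it

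*SAP*

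**What the plan says.** **When treatment and scans stop.** Protocol 5.1.2 (Treatment Duration) ties the end of treatment to one reading: "Subjects will continue taking MSC2156119J until PD [as assessed by the investigator according to Response Evaluation Criteria in Solid Tumors (RECIST) Version 1.1". Protocol 7.1.3.7 schedules scans before Cycles 3, 5, 7, 9, 11 and 13 and "every 4 cycles thereafter until disease progression or study drug discontinuation". Protocol 5.5.2 and 7.1.5 continue off-treatment scans only for subjects who stopped for a reason other than progression. For those who stopped for progression, trial procedures close at the post-treatment visit. SAP 16.1 repeats that scans run until PD. Nothing extends scanning until PD by mRECIST or by the IERC.

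**Which analyses reuse the rule.** Phase II SAP 16.2.1 states: "The analysis of PFS per investigator as assessed by RECIST 1.1 and mRECIST will be performed using the following methods". SAP 16.2.2 does the same for mRECIST TTP. SAP 16.4.1 adds: "Overall summary tables per the IERC for both RECIST 1.1 and mRECIST will be produced for PFS and TTP", as a sensitivity analysis to the primary and secondary endpoints.

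**The censoring rule.** Without an event, time is censored at the last CR, PR, Non-CR/non-PD or SD result. For PFS, death within 12 weeks of that assessment is an event. For TTP, death is not an event.

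**The concern.** Take a subject whose investigator calls RECIST 1.1 PD while mRECIST, or the IERC, reads stable disease on the same images. The subject leaves the risk set at the moment one reader judged the tumour to be progressing. Later PD on the other reading cannot be seen. Kaplan-Meier treats the subject as typical of those still at risk, although such a subject is probably closer to PD than they are.

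Protocol Appendix K makes discordance concrete. An atypical new liver lesion is called HCC only after growth on later scans, and progression is then dated back to first detection. Those scans are not scheduled after RECIST 1.1 PD.

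The stake is interpretive. mRECIST PFS is a named secondary endpoint (Protocol 8.3.2.1), and the IERC curves are the stated check on investigator reading in an open-label, single-arm trial. A check that tends to look favourable is a weak one.

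**Working it through.** **1. The plan's own figure.** Protocol 8.1 gives a null rate that "was assumed to be ~15% based on historical data", an error rate ("With a type I error rate of 5% (one-sided") and a target ("to reach a power of 80% if the true rate of subjects without progression at 12 weeks is 30"), and concludes that "this design requires 48 subjects to be treated in Phase II". With rejection at 12 or more:

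- P(X >= 12 | n = 48, p = 0.15) = 0.0478
- P(X >= 12 | n = 48, p = 0.30) = 0.8186 (0.794 at n = 47)

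The design reproduces. It counts investigator RECIST 1.1 status only, so the present point does not touch it.

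**2. One subject traced.** At week 12 the investigator calls RECIST 1.1 PD and mRECIST reads SD. Scans stop.

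- mRECIST TTP: censored at week 12.
- mRECIST PFS: an event if death comes by week 24, otherwise censored at week 12.
- mRECIST PD that would have been seen at week 18: never observed.
- In the reverse order (mRECIST PD at week 6, RECIST 1.1 SD), the mRECIST event is captured.

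**3. TTP in closed form.** The assumptions, none from the documents, are a constant investigator-PD probability h per 6-week scan, a share d of those PDs not PD on the other reading, and a geometric delay with mean m scans to PD on that reading. No deaths are modelled. The last scan before 6 months is week 24, the fourth.

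- SAP rule: (1 - h(1 - d))^4
- Full follow-up: (1 - h)^4 + sum over k = 1 to 4 of (1 - h)^(k-1) · h · d · (1 - 1/m)^(4-k)
- Discordant subjects counted as events: (1 - h)^4

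Example: a latent median of 8 weeks gives h = 1 - 2^(-6/8) = 0.405. With d = 0.20, the SAP rule gives (1 - 0.324)^4 = 20.8%. Full follow-up gives 14.2% (m = 1) or 17.9% (m = 2). Counting as events gives 12.5%.

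| Investigator PD assumption | d | SAP rule | Full follow-up (m = 1, 2) | Gap, points |
|---|---|---|---|---|
| Median 8 weeks | 0.20 | 20.8% | 14.2%, 17.9% | 6.6, 3.0 |
| Median 12 weeks | 0.30 | 39.9% | 28.1%, 33.0% | 11.8, 7.0 |
| 30% progression-free at 12 weeks | 0.20 | 16.6% | 10.5%, 14.2% | 6.1, 2.4 |
| 30% progression-free at 12 weeks | 0.30 | 21.8% | 11.2%, 16.8% | 10.6, 5.0 |
| 15% progression-free at 12 weeks | 0.20 | 6.8% | 3.0%, 6.6% | 3.8, 0.2 |
| 15% progression-free at 12 weeks | 0.30 | 10.6% | 3.3%, 8.8% | 7.3, 1.9 |

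Medians of 8 and 12 weeks imply 2^(-12/8) = 35% and 2^(-12/12) = 50% progression-free at 12 weeks, above the protocol's 15% to 30%. The gap nearly vanishes in the fifth row at m = 2 because the discordant subjects' PD probability per scan (1/2) is close to that of the rest at risk, h(1 - d) = 0.613 × 0.8 = 0.490. The bias exists only to the extent that discordant subjects are nearer to PD.

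**4. Two-way discordance with deaths.** Simulation on the protocol scan grid, 200,000 subjects per scenario. Assumed: 12-week progression-free rate 15% or 30%, median OS 6 or 9 months, correlation between criteria 0 to 0.9, PD-death correlation 0 or 0.4. Entries are stopped scans minus continued scans, in points.

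| | Correlation 0.3 to 0.9 | Independent criteria |
|---|---|---|
| TTP, 3 months | +1.8 to +4.0 | about 0 |
| TTP, 6 months | +1.1 to +5.8 | about 0 |
| PFS, 3 months | +0.6 to +3.0 | 0 to -1.2 |
| PFS, 6 months | -0.9 to +3.4 | -0.8 to -2.3 |

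With correlation 0.3 to 0.9, 10% to 30% of subjects were discordant, which is 5 to 14 of 48. Across all scenarios, 13% to 28% of discordant subjects became PFS events through the 12-week death rule.

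**5. One-way discordance with the death rule.** With step 3's 8- to 12-week medians, and death independent of PD, the 6-month gap is +3.0 to +11.8 points for TTP and +0.5 to +5.7 for PFS.

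**6. Combined range at 6 months, positive correlation.** TTP from +1.1 (step 4) to +11.8 (step 5). PFS from -0.9 (step 4) to +5.7 (step 5).

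**The case against.** - **PFS does not always censor at that scan.** Subjects who die within 12 weeks of the discordant scan are events. This stands. It shrinks the PFS effect and can reverse its sign.
- **The other reading can progress first.** mRECIST measures viable tumour against its own smallest sum, and an IERC may call PD earlier. Scans are then still running and the event is captured. A reader might infer that the mRECIST and IERC curves must look better than RECIST 1.1 by construction. The documents do not support that.
- **Medians.** A reader might infer that the median shifts by a whole scan. It can with an assumed 8-week median and d = 0.30, where the week-12 value is 51.3% against 42.6% to 48.7%, only just across 50% on a 6-week grid. At the protocol's 15% and 30% rates, step 3 gives 12 weeks under both rules in every setting. In step 4 no median rose.
- **Partial mitigation exists.** SAP 16.2.1 summarises the censoring pattern with an open list of examples, response data are listed, 16.4.1 cross-tabulates BOR, and Appendix J allows equivocal progression to be followed to the next scan. None of this names or counts the discordant censorings, and BOR agreement does not show PD status or date.
- **Reach.** These are descriptive secondary and sensitivity curves. That limits the weight of the point but does not remove it.

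**Conclusion.** The point holds in a limited form. Scanning stops on one reading while Kaplan-Meier curves on other readings censor there, and neither document addresses it.

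TTP by mRECIST and by IERC is biased upward under any positive correlation between the criteria, which is likely since the same scans are read. Under the assumed inputs the size is roughly +1 to +12 points at 6 months. PFS is affected less, roughly -1 to +6 points, and the direction is not certain. A reader might carry the TTP range over to PFS; the 12-week death rule is why that is wrong.

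Discordance rate, delay, correlation and survival are all assumptions, so these figures show plausible size and are not predictions. The primary binomial test and the investigator RECIST 1.1 PFS and TTP are unaffected.

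**What to change.** In Phase II SAP 16.2.1, 16.2.2 and 16.4.1, for every mRECIST and IERC PFS and TTP table:

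1. Report, as its own censoring reason with its count, that scans ended at investigator RECIST 1.1 PD without PD by this criterion.
2. Show beside the table a sensitivity analysis counting these subjects as events at the investigator PD date. Label it a conservative composite of investigator RECIST 1.1 PD or PD by this criterion, because it is not mRECIST or IERC PFS/TTP itself.

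The two estimates then bracket the result; in step 3's example, 12.5% and 20.8% around 14.2% to 17.9%. For PFS the upper end is approximate, since the sign is uncertain.

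The cost is one extra run per table, using data already collected, and a less favourable companion estimate.

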16.2.2 Time to Progression (TTP)

TTP will be measured as the time (in months) from the date of first trial treatment administration to the date of radiological confirmation of PD performed according to RECIST Version 1.1. TTP will be censored at the date of last adequate tumor assessment for subjects that do not experience progression or subjects that experience progression after 2 or more subsequent missing tumor assessments. Subjects that are missing a baseline tumor assessment and/or all post-baseline tumor assessments will be censored at the first date of trial treatment administration.

The date of event/censoring is defined as follows:

Status		Censoring	Date of event / censoring	
	Radiological PD	Event	Date of PD	
Progressed	Otherwise	Censored	Date of last tumor assessment with outcome CR, PR, Non-CR/non-PD, o SD or date of first study drug administration, whatever is later	
Didn't progre	ess	Censored	Date of last tumor assessment with outcome CR, PR, Non-CR/non-PD, or SD or date of first study drug administration, whatever is later	

TTP (months) = (date of PD/censoring – date of first trial treatment administration + 1)/30.4375

The analysis of TTP per investigator as assessed by RECIST 1.1 will be performed using Kaplan-Meier methods with the same approach for PFS described in Section 16.2.1. TTP per investigator as assessed by mRECIST will be analyzed using the same methods as the analysis of TTP per investigator as assessed by RECIST 1.1.

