#### 8.3.2 Secondary Endpoints

#### 8.3.2.1 Efficacy Endpoints

Secondary endpoints are as follows:

• TTP, measured as the time (in months) from the date of first study drug administration to the date of radiological confirmation of PD performed according to RECIST Version 1.1. In HCC, TTP is recommended as a sensitive endpoint in measuring antitumor activity of molecularly targeted agents in HCC Phase II trials since it is less vulnerable to the potential confounding effect of underlying liver disease than the traditional endpoint PFS. For this reason, TTP will be regarded as the major sensitivity analysis for the primary endpoint of PFS status.

- PFS, defined as the time (in months) from first study drug administration to either first observation of PD (as assessed by RECIST Version 1.1) or occurrence of death due to any cause within 12 weeks of the last tumor assessment, whichever occurs first.
- PFS, defined as the time (in months) from first study drug administration to either first observation of PD (as assessed by mRECIST for HCC) or occurrence of death due to any cause within 12 weeks of the last tumor assessment, whichever occurs first.
- Time-to-symptomatic progression (TTSP) as subject-reported outcome, defined as the time (in months) from first study drug administration to the date of deterioration of symptoms assessed by FHSI-8 (defined as at least a 4-point increase, i.e., higher score, compared with baseline value), or deterioration to ECOG performance score 4, or death (applicable for Phase II only).
- OS time, defined as the time (in months) from first study drug administration to the date of death.
- Objective tumor response: Subjects with best overall tumor assessment of CR or partial response according to RECIST Version 1.1 from first study drug administration until first occurrence of PD.
- Disease control: Subjects with best overall tumor assessment of CR, partial response, or SD according to RECIST Version 1.1 from first study drug administration until first occurrence of PD. SD must be observed at the end of Cycle 2 or later.
- Biological response as measured by serum AFP, defined as a > 20% decrease in AFP level by Cycle 2 compared with baseline.

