# 8.5.3 Analysis of Secondary Endpoints

#### 8.5.3.1 Time-to-Event Endpoints

TTP will be measured as the time (in months) from the date of first study drug administration to the date of radiological confirmation of PD performed according to RECIST Version 1.1. Deaths or subjects without radiological progression at time of analysis will be censored at the date of last tumor assessment.

PFS is defined as the time (in months) from first study drug administration to either first observation of PD or occurrence of death due to any cause within 12 weeks of the last tumor assessment, whichever occurs first. If no progression or death is observed, or if death without previously documented PD is observed more than 12 weeks after last tumor assessment without progression, PFS will be censored at the date of last tumor assessment or first administration of MSC2156119J, whichever occurs later.

TTSP as a subject-reported outcome is defined as the time (in months) from first study drug administration to the date of deterioration of symptoms assessed by FHSI-8 (defined as at least a 4-point increase, i.e., higher score, compared with baseline value), or deterioration to ECOG performance score 4, or death.

OS will be measured as the time (in months) from first study drug administration to the date of death. For subjects not known to be deceased at time of analysis, OS time will be censored at the last date the subject was known to be alive. If this date is after the data cutoff, subjects will be censored at the date of data cutoff.

TTP, PFS, TTSP and OS will be analyzed by Kaplan-Meier estimates as appropriate.

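### Phase II TTP censors deaths without progression and has no competing-risk estimate, so its 3-month figure cannot check the primary result against those deaths; cumulative incidence is a cheap addition

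*SAP*

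**What the plan says.** Protocol 8.3.2.1 states that "TTP will be regarded as the major sensitivity analysis for the primary endpoint of PFS status". Its reason is that TTP is "less vulnerable to the potential confounding effect of underlying liver disease than the traditional endpoint PFS".

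Protocol 8.5.3.1 handles deaths explicitly: "Deaths or subjects without radiological progression at time of analysis will be censored at the date of last tumor assessment". Phase II SAP 16.2.2 does not name deaths but reaches the same result: "TTP will be censored at the date of last adequate tumor assessment for subjects that do not experience progression". Subjects with no post-baseline scan "will be censored at the first date of trial treatment administration".

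On estimation, SAP 16.2.2 says the TTP analysis "will be performed using Kaplan-Meier methods with the same approach for PFS described in Section 16.2.1". That section states that "Kaplan-Meier estimates of survival probability at 3, 6, and 12 months will be estimated", with 90% CIs, a median, a plot and a summary of censoring reasons. Neither document plans a cumulative-incidence or other competing-risk analysis of TTP.

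The primary endpoint treats the same subjects differently. Under protocol 8.3.1 and 8.5.2, anyone without a qualifying scan at 12 weeks or later is not progression-free and stays in the denominator of all treated subjects.

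**The concern.** A subject who dies without PD can no longer progress. Kaplan-Meier treats that subject as ordinary censoring, as if the dead kept the survivors' progression hazard. Someone who dies before the Cycle 3 scan is censored at first dose and contributes nothing to the curve.

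Two consequences follow, against different comparators, and they should be kept apart:

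- **(a) Against the incidence of PD.** 1 - KM at 3, 6 and 12 months is larger than the proportion of treated subjects who progress.
- **(b) Against the primary proportion.** Near 12 weeks, meaning the 3-month estimate, each death without PD is a primary failure but drops out of the TTP risk set. KM TTP therefore tends to sit above the primary rate, and it cannot show whether the primary result is robust to those deaths.

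What is at stake is interpretation. A reader who sets the 3-month TTP figure beside the primary rate and the 15% null could take the difference as support for activity when it comes only from removing deaths.

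**Working it through.** **The plan's own figure.** The documents give no TTP figure. The design figure reproduces: with 48 subjects and a cut-off of 12, the exact binomial type I error at 15% is 0.0478 and the power at 30% is 0.819. With 47 subjects and the same cut-off, power is 0.794. None of this involves TTP.

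**Inputs.** From the documents: N = 48, a primary rate S of 30% or 15%, and scans before Cycles 3 and 5 (weeks 6 and 12). Assumed, because the documents give no value: a proportion d of 5%, 10% or 20% dying without PD by week 12, and 60% of PD found at the first scan. Death is placed either before the first scan or between the two scans. There is no other dropout.

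**Formulas.** PD incidence = 1 - S - d. PD at scan 1 is q = 0.6 x (1 - S - d).

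- Deaths before scan 1 (censored at first dose): KM = S / (1 - d).
- Deaths between scans (censored at scan 1): KM = (1 - q) x S / (1 - q - d).

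Example, S = 30%, d = 10%: 0.30/0.90 = 33.3%, or, with q = 0.36, 0.64 x 0.30/0.54 = 35.6%.

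| S | d | Deaths | KM TTP | KM - S | 1 - KM | PD incidence | Excess of 1 - KM |
|---|---|---|---|---|---|---|---|
| 30% | 5% | before scan 1 | 31.6 | 1.6 | 68.4 | 65 | 3.4 |
| 30% | 5% | between scans | 32.7 | 2.7 | 67.3 | 65 | 2.3 |
| 30% | 10% | before scan 1 | 33.3 | 3.3 | 66.7 | 60 | 6.7 |
| 30% | 10% | between scans | 35.6 | 5.6 | 64.4 | 60 | 4.4 |
| 30% | 20% | before scan 1 | 37.5 | 7.5 | 62.5 | 50 | 12.5 |
| 30% | 20% | between scans | 42.0 | 12.0 | 58.0 | 50 | 8.0 |
| 15% | 5% | before scan 1 | 15.8 | 0.8 | 84.2 | 80 | 4.2 |
| 15% | 5% | between scans | 16.6 | 1.6 | 83.4 | 80 | 3.4 |
| 15% | 10% | before scan 1 | 16.7 | 1.7 | 83.3 | 75 | 8.3 |
| 15% | 10% | between scans | 18.3 | 3.3 | 81.7 | 75 | 6.7 |
| 15% | 20% | before scan 1 | 18.75 | 3.75 | 81.25 | 65 | 16.25 |
| 15% | 20% | between scans | 22.3 | 7.3 | 77.7 | 65 | 12.7 |

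As a check, the two gaps in each row add up to d, since (KM - S) + [(1 - KM) - (1 - S - d)] = d. Kaplan-Meier shares the deaths out between progressed and progression-free.

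**At the decision boundary.** Take 12 of 48 progression-free (25.0%), with 2, 5 or 10 of the 36 failures dying before any scan and the rest progressing by week 12. KM TTP is 12/46, 12/43 or 12/38 = 26.1%, 27.9% or 31.6%. 1 - KM is 73.9%, 72.1% or 68.4%, against PD incidence of 34/48, 31/48 or 26/48 = 70.8%, 64.6% or 54.2%.

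**Later landmarks.** A simulation of the Phase II rules used constant hazards, with death making up 5% to 30% of the total hazard and a true primary rate of 30%. At 6 months, 1 - KM was 0.90 to 0.81 against a PD cumulative incidence of 0.85 to 0.57. At 12 months it was 0.99 to 0.97 against 0.93 to 0.63. KM TTP itself was 0.10 to 0.19 at 6 months and 0.01 to 0.03 at 12 months.

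**The case against.** The strongest reply is that setting deaths aside is the purpose of TTP here. The protocol chose it to look at antitumor activity apart from liver-related death, so censoring deaths is a reasoned definition and not an SAP error. That stands. The addition below supplements the definition and does not correct it.

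Much of the information is also planned elsewhere:

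- SAP 16.2.1 analyses PFS with deaths within 12 weeks of the last adequate scan as events, at the same landmarks.
- The Kaplan-Meier approach that TTP inherits includes numbers at risk and a censoring summary in which death is a category.
- SAP 16.1 reports PD or death by 12 weeks with an exact CI.
- SAP 17.2.1 tabulates deaths, including those within 60 days of first dose.

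A gap between TTP and PFS would therefore be visible. What is missing is the split of failures into PD and death without PD at each landmark, and a stated count of such deaths by week 12.

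The death rate is assumed. Entry requires Child Pugh A, ECOG 0-1 and at least 3 months' life expectancy, and nothing in the documents supports the 20% end. At 30% with 48 subjects, the 90% CI half-width is about 1.645 x sqrt(0.30 x 0.70/48) = 11 points, larger than most of the shifts in (b).

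Stronger readings are tempting but are not supported:

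- A reader might infer that all three landmark values flatter the drug against the primary endpoint by construction. The primary endpoint is a 12-week status, so the 6- and 12-month values have no counterpart; in the simulation they fall well below 30%. Even at 3 months, the excess is zero without deaths, dropout or missing scans.
- A reader might infer that the trial's conclusion is at risk. No decision rule uses TTP. The Phase II SAP does not repeat the sensitivity label; the sensitivity analysis it names is the independent review in 16.4.1.
- The Phase Ib SAP has similar TTP censoring, but its primary endpoint is DLT incidence, so the comparison in (b) does not arise there.

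**Conclusion.** The point holds as a cheap improvement for Phase II. The analysis that the protocol names to check the primary endpoint removes some of that endpoint's failures, and no planned TTP output gives the proportion of treated subjects who progress.

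If 5% to 20% die without PD by week 12, KM TTP exceeds a 30% primary rate by about 1.6 to 12 points. At a 15% rate the excess is smaller: 1.7 to 3.3 points at 10% deaths and 3.8 to 7.3 at 20%. The excess of 1 - KM over PD incidence at 10% deaths is 4.4 to 6.7 points (30% rate) or 6.7 to 8.3 points (15% rate).

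These sizes rest on the assumed death rate and its timing and, for deaths between scans, on the 60% share of PD at the first scan. The direction of (a) does not depend on those values as long as some such deaths occur. The exact test and the 12-of-48 rule are unaffected.

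**What to change.** In Phase II SAP 16.2.2:

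- Keep the Kaplan-Meier TTP analysis as planned.
- Add the Aalen-Johansen cumulative incidence of radiological PD and of death without prior PD at 3, 6 and 12 months, with 90% CIs. Count death as a competing event at its date.
- Report the number of deaths without PD by week 12.
- State that 1 - KM is not the proportion progressed.
- Use the cumulative-incidence pair whenever TTP is set against the primary 12-week rate.

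The dates of PD and death are already collected for TTP and OS, so the cost is SAP wording, one table and one plot. The downside is a second TTP summary to explain beside the conventional one. No change to the Phase Ib SAP is needed for this point.
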